2. SYNOPSIS

Name of Sponsor/Company: Mezzion Pharma Co. Ltd in partnership with Pediatric Heart Network (PHN)	Individual Study Table Referring to Part of the Dossier Volume: Page:	(For National Authority Use Only)
Name of Finished Product: Udenafil tablet 87.5 mg		
Name of Active Ingredient: Udenafil		
Title of Study: A Phase III Safety Extension Study of Udenafil in Adolescents with Single Ventricle Physiology After Fontan Palliation (FUEL Extension)		
Principal Investigator: Multicenter		
Investigators: A list of investigators and their curricula vitae are provided in Appendix 16.1.4 .		
Study center(s): 27 sites (25 United States, 2 Canada)		
Publications (reference): None		
Studied period (years): Date of first informed consent: 06 February 2017 Date of data cutoff: 31 August 2020	Phase of development: 3	
Objectives: 
Determine the safety of udenafil (87.5 mg twice daily [BID]) in an adolescent population with single ventricle congenital heart disease palliated with the Fontan procedure.Evaluate the pharmacodynamic profile of udenafil.		

Methodology:

This was a Phase 3, open-label extension, 12-month, multicenter study, with an option for up to an additional 36 months, to supplement the Phase 3 **Fontan Udenafil Exercise Longitudinal Assessment Trial (FUEL study)** by providing a more robust safety and side-effect profile of the use of udenafil in adolescents with Fontan physiology. An attempt was made to recruit all participants who completed the FUEL study (approximately 400 adolescents). If recruitment from the FUEL study was less than 300 subjects, additional adolescents with Fontan physiology (De Novo subjects) were identified through the review of clinical data records at each participating site until the minimum of 300 total subjects were enrolled.

Those who were interested were enrolled and consented at the first study visit by the study coordinator from each participating site. Screening and identification of potential subjects continued until enrollment was complete.

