
Statistical methods at interim analysis: The Safety population included all subjects who took at least 1 dose of study drug. The Efficacy population included all enrolled subjects who had baseline and Week 52 exercise capacity data for which site-based data quality assurance process was complete at data cut-off.

Three treatment groups were defined:
 
• Udenafil-Udenafil, which included subjects who received udenafil in the FUEL and FUEL Extension studies• Placebo-Udenafil, which included subjects who received placebo in the FUEL study and udenafil in FUEL Extension• De Novo: Subjects who did not participate in the FUEL study and received udenafil in FUEL Extension

For efficacy and safety summaries, the Placebo-Udenafil and De Novo groups were combined (denoted as Placebo/De Novo-Udenafil).

All summaries were descriptive. Descriptive statistics for categorical endpoints included the number and percent of subjects in each treatment group and category. Quantitative endpoints were summarized for each treatment group with the mean, median, standard deviation, minimum value, and maximum value. Missing data were not imputed.

Baseline was defined as the last measurement before receipt of udenafil in FUEL Extension. For the Udenafil-Udenafil group, change to Week 52 of FUEL Extension measures change in exercise capacity between 26 weeks and 78 weeks of udenafil treatment. This change represents persistence of initial effectiveness beyond 26 weeks. For the Placebo-Udenafil and De Novo groups, change to Week 52 of FUEL Extension measures change in exercise capacity from pre-udenafil to following 52 weeks of udenafil treatment.

Statistical methods (continued):

For each efficacy endpoint, descriptive statistics were summarized for baseline, Week 52, and Week 52 change from baseline. A 2-sided, 95% confidence interval was calculated for change from baseline for each group.

Safety analyses were descriptive with no formal hypothesis testing. All AEs were classified by the Medical Dictionary for Regulatory Activities with respect to system organ class and preferred term. Subject incidence of all treatment-emergent adverse events (TEAEs), and TEAEs that are treatment-related, serious, serious treatment-related, and any TEAE leading to study discontinuation were tabulated. Number (%) of subjects who were hospitalized, had a cardiac transplant, or died were tabulated.

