No clinically important differences were observed in the safety profile between subjects who had previously received treatment with udenafil and those who were naïve to udenafil treatment prior to participating in this study.

Similar percentages of subjects in the Udenafil-Udenafil and Placebo/De Novo-Udenafil groups reported TEAEs (77.3% and 80.3%, respectively), drug-related TEAEs (64.1% and 67.6%, respectively), TEAEs of Grade ≥ 3 (3.9% and 7.5%, respectively), serious TEAEs (10.9% and 13.9%, respectively), drug-related serious TEAEs (3.9% and 5.8%, respectively), and TEAEs resulting in temporary or permanent discontinuation of study drug (15.6% and 12.7%, respectively).

The most common TEAEs reported included headache (35.2%), flushing (17.2%), dizziness (11.7%), upper respiratory tract infection (10.2%), and nausea (10.2%) in the Udenafil-Udenafil group and headache (40.5%), flushing (15.6%), nasopharyngitis (12.7%), and dizziness (12.7%) in the Placebo/De Novo-Udenafil group. Most TEAEs were mild or moderate in intensity; similar percentages of subjects in the Udenafil-Udenafil (5 subjects; 3.9%) and Placebo/De Novo-Udenafil (13 subjects; 7.5%) groups experienced a severe TEAE.

There was no clinically important difference in the TEAE profile among males and females; the limited number of non-Caucasian subjects and Hispanic or Latino/Latina subjects precluded meaningful comparisons between race and ethnicities within treatment groups.

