9.4.3 Method of Assigning Subjects to Treatment Groups

Randomization assignments were generated by a web-based system at the DCC, after confirmation of study eligibility. Eligible subjects were stratified by ventricular morphology (single left vs single right or mixed) and randomly assigned to udenafil or placebo.

The randomization codes and treatment assignments by subject number are provided in [Appendix 16.1.7](#).

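### The FUEL Extension synopsis merges former placebo subjects with never-randomised De Novo subjects and restarts baseline at extension entry, so it reports no comparison by original FUEL arm

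*Protocol*

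**What the plan says.** The extension is described only in section 2 (Synopsis) of the protocol document. The body of that document and the SAP cover the 26-week FUEL trial.

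- **Groups.** "Three treatment groups were defined": Udenafil-Udenafil, Placebo-Udenafil and De Novo. The last is "De Novo: Subjects who did not participate in the FUEL study and received udenafil in FUEL Extension". De Novo recruitment was a top-up: "If recruitment from the FUEL study was less than 300 subjects, additional adolescents with Fontan physiology (De Novo subjects) were identified".
- **Pooling.** "For efficacy and safety summaries, the Placebo-Udenafil and De Novo groups were combined". The results give only Udenafil-Udenafil and the pooled group.
- **Baseline.** "Baseline was defined as the last measurement before receipt of udenafil in FUEL Extension". For Udenafil-Udenafil this is the value after about 26 weeks on drug; for the other two groups it is pre-drug.
- **Analysis.** Everything is descriptive, with a 95% CI for each group's own change. The Efficacy population needs paired baseline and Week 52 data, and nothing is imputed.
- **Conclusions drawn.** On safety: "No clinically important differences were observed in the safety profile between subjects who had previously received treatment with udenafil" and those new to the drug. On the Udenafil-Udenafil change from week 26 to week 78: "This change represents persistence of initial effectiveness beyond 26 weeks". The synopsis conclusion repeats the persistence claim.
- **Parent trial.** Subjects were "randomly assigned to udenafil or placebo" (section 9.4.3), 200 per arm. Table 5 shows 126 (63.0%) and 124 (62.0%) continuing into the extension.

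**The concern.** Udenafil-Udenafil and Placebo-Udenafil descend from arms randomised against each other, and both have a pre-drug FUEL baseline. De Novo subjects have neither feature. Two choices then obscure what the FUEL arms could show.

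First, when De Novo is folded into the former placebo group, a reader cannot tell whether a difference from Udenafil-Udenafil reflects prior treatment or who the added subjects were. The safety statement compares exactly these two columns.

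Second, the restarted baseline gives the two columns different meanings. One is change while staying on drug; the other is change from off drug to on drug. Neither has a concurrent untreated control. In growing adolescents, such changes mix growth, natural decline and any drug effect. Section 9.8.2.3 itself notes that weight gain alone can make VO₂ per kg appear to fall. Persistence is nevertheless concluded from the Udenafil-Udenafil column alone.

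**Working it through.** **1. Group sizes.** The synopsis gives counts with percentages.
- Udenafil-Udenafil: 14 = 10.9%, 20 = 15.6%, 5 = 3.9%. The only whole number that fits all three is 128.
- Pooled group: 24 = 13.9%, 22 = 12.7%, 13 = 7.5%. The only fit is 173.
- 128 + 173 = 301, which reproduces the stated safety N.

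**2. Size of De Novo.** The split of 173 is not given.
- With Table 5's 124 placebo continuers: 173 − 124 = 49 (28%).
- With Table 5's total of 250 and 128 in Udenafil-Udenafil: 122 Placebo-Udenafil and 51 De Novo (29%).
- With an assumed upper value of 128 placebo continuers: 45 De Novo (26%).

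The 128 found in step 1 does not match the 126 udenafil continuers in Table 5.

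**3. What pooling can hide.**
- Efficacy: if mean change in De Novo differed from Placebo-Udenafil by 1 mL/kg/min (assumed), the pooled mean would move by 0.26 to 0.29.
- Safety: the 13 pooled subjects with Grade 3 or higher events could be 5/124 (4.0%) and 8/49 (16.3%), or 13/124 (10.5%) and 0/49. The first matches the 3.9% in Udenafil-Udenafil; the second does not. The synopsis cannot separate them. The same holds for the 4 subjects with serious cardiac failure.

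**4. What the restarted baseline does.** Let g be the common trend over the 52 extension weeks and d a drug effect reached by week 26 and then constant.

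| | From extension entry | From FUEL baseline (h = trend over the first 26 weeks) |
|---|---|---|
| Udenafil-Udenafil | g | h + g + d |
| Placebo-Udenafil | g + d | h + g + d |
| Difference | −d | 0 |

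Side by side, the extension changes make an effective drug look worse in the early-start group. From the FUEL baseline, the week-78 difference is 0 under a constant effect and also 0 if d = 0. It is positive only if starting early brought an added benefit.

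The reported changes in maximal VO₂ are −1.45 (−2.3 to −0.6) and −0.93 (−1.7 to −0.2) mL/kg/min.
- Difference: −1.45 − (−0.93) = −0.52.
- SEs from the rounded CIs: 0.85/1.96 = 0.434 and 0.75/1.96 = 0.383. Combined SE = √(0.434² + 0.383²) = 0.578.
- Approximate 95% CI: −1.65 to 0.61.
- Adding FUEL's week-26 difference of 0.64 gives about 0.12 at week 78. This is crude: it treats De Novo like Placebo-Udenafil and applies the full-trial difference to continuers.

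**5. Precision of a difference by FUEL arm.** Two routes:
- *FUEL SD.* Table 13 gives SDs of change of 4.056 and 3.672, so the pooled SD is √((4.056² + 3.672²)/2) = 3.869. Assume the same SD at week 78. Half-width = 1.96 × 3.869 × √(1/n₁ + 1/n₂): 0.96 for 126 versus 124, 1.07 for 100 per group, 1.20 for 80 per group.
- *Reported CIs.* Half-widths are 0.85 (Udenafil-Udenafil) and 0.75 (pooled). With De Novo at 26% to 29% and a similar SD, Placebo-Udenafil alone has 0.75/√0.74 = 0.87 to 0.75/√0.71 = 0.89. Combined: √(0.85² + 0.87²) = 1.22 to √(0.85² + 0.89²) = 1.23. Rounding of the published limits widens this to about 1.1 to 1.3.

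At SD 3.869, a half-width of 0.85 implies (1.96 × 3.869/0.85)² ≈ 80 Udenafil-Udenafil subjects with paired data, so the 0.96 end is optimistic. Even with 124 per group, power to see a difference of 0.64 is about 26%.

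**The case against.** The extension is an open-label safety study. Its objectives are safety and pharmacodynamics, and no between-group efficacy estimate is reported. The pooling has a logic: both merged groups are udenafil-naive with a pre-drug baseline, and the synopsis says plainly what each group's change measures. Early versus delayed start is a question added from outside. De Novo subjects share FUEL's age range and also needed a maximal-effort exercise test, and FUEL subjects too were found by chart review.

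Much of this stands, and it rules out three stronger readings that a reader might infer:

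- *That the extension threw away its only randomised comparison.* The three groups remain defined and the FUEL baselines exist. The contrast is unreported in an interim synopsis; the extension's own protocol, SAP and full tables are not among the documents. Nor would it be a fully randomised comparison: 74 udenafil and 76 placebo subjects did not continue, continuing was by choice, and efficacy is complete-case. Similar rollover rates do not show that the continuers are alike.
- *That De Novo subjects do confound the results.* No baseline comparison is shown, so confounding is possible but not demonstrated.
- *That a VO₂ model by FUEL arm would settle both conclusions.* It cannot support a statement about adverse events, and by step 4 a week-78 difference near zero fits both a constant effect and no effect.

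The objection does not reach the conclusions themselves. The synopsis does compare previously treated with naive subjects on safety, and does claim persistence. Descriptive tables can carry three columns as easily as two.

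**Conclusion.** The point holds as one of reporting and interpretation. Roughly 26% to 29% of the pooled group was never randomised (assuming 122 to 128 former placebo subjects), and the synopsis gives no result by original FUEL arm. The safety statement may be affected by De Novo case mix, and the persistence conclusion rests on uncontrolled change from an on-drug baseline. For Placebo-Udenafil, the extension baseline does suit the within-group question; the restart harms the between-group reading and the interpretation of Udenafil-Udenafil.

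A difference by FUEL arm would be informative but imprecise: a half-width of about 1.0 to 1.3 mL/kg/min, assuming an SD near 3.9 or the reported CI widths. It belongs in the report as a description with its CI, not as a test. This should be changed because it costs little and alters what can be concluded.

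**What to change.** - **All tables.** Show Udenafil-Udenafil, Placebo-Udenafil and De Novo in separate columns for every efficacy and safety summary. A pooled naive column may stay beside them.
- **Efficacy.** Add the Udenafil-Udenafil minus Placebo-Udenafil difference, with 95% CI, in change from the pre-drug FUEL baseline to extension Week 52, adjusted for FUEL baseline and ventricular morphology. Label it an early-versus-delayed-start contrast among continuers with paired data. Accompany it with a comparison of continuers and non-continuers and a missing-data sensitivity analysis.
- **Safety.** Rest the previously-treated-versus-naive statement on the separate adverse-event columns. State that Udenafil-Udenafil subjects had already been through 26 weeks on drug and chose to continue, so those who tolerated it poorly may be under-represented.
- **Persistence.** Qualify the claim: within-group change is uncontrolled, and a week-78 difference near zero would not settle it.
- **Counts.** Reconcile the 128 Udenafil-Udenafil subjects implied by the percentages with the 126 continuers in Table 5, and state the De Novo number.

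The cost is extra columns, one model and two supporting analyses on data already held, with no new visits or subjects. The drawback is rollover and complete-case selection, which must be stated beside the result.

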In-clinic study visits included assessments of safety (AEs, concomitant medication use, vital signs, and clinical safety laboratory evaluations), efficacy (exercise testing, echocardiogram, EndoPAT®, brain natriuretic peptide, and quality of life measurements), and pharmacokinetics.

The duration of study drug dosing was 12 months, with an option to extend for up to an additional 36 months. When an individual subject completed the study, the subject's primary cardiologist was notified, and the study drug was stopped.

De Novo subjects who were not participants in the FUEL trial were given the opportunity to participate in the heart rhythm-monitoring subset of FUEL Extension. Optional heart rhythm monitoring was to include a 3- to 7-day baseline monitor and a 3-day steady-state monitor.

Number of patients (planned and analyzed):

Planned: 300 to 400 adolescents.

Analyzed: 301 adolescents for safety (at interim analysis).

Diagnosis and main criteria for inclusion:

1. Males and females with Fontan physiology who participated in the FUEL trial or, if they did not participate in FUEL, were 12 to less than 19 years of age at enrollment.
2. Current anti-platelet or anticoagulant therapy.

Test product, dose and mode of administration, batch number: Udenafil tablets 87.5 mg orally BID [name] Ltd.: Batches UDBT15-11 and UDBT15-12 Halo Pharmaceutical Canada, Inc.: Batch MP0220

Duration of treatment: 52 weeks, with an option to extend for up to an additional 36 months

Reference therapy, dose and mode of administration, batch number: None

Criteria for evaluation at interim analysis: Efficacy endpoints:
 
• Change in maximal VO₂ from baseline to Week 52• Change in VO₂ at ventilatory anaerobic threshold (VAT) from baseline to Week 52• Change in ventilatory equivalents of carbon dioxide (VE/VCO₂) at peak exercise from baseline to Week 52• Change in VE/VCO₂ at VAT from baseline to Week 52• Change in minute ventilation at peak exercise• Change in work rate at peak exercise from baseline to Week 52• Change in work rate at VAT from baseline to Week 52• Change in myocardial performance index (MPI) from baseline to Week 52

Safety: Adverse events, vital signs (blood pressure and heart rate), and concomitant medication use.

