Incidence of potentially clinically significant changes from pre dose values in blood pressure and heart rate were tabulated at i) post first study dose but before the self-limited 6-minute walk, ii) after the 6-minute walk, and iii) at any time after dosing.

SUMMARY – CONCLUSIONS

EFFICACY RESULTS:

For the Udenafil-Udenafil group, change to Week 52 of FUEL Extension measures change in exercise capacity between 26 weeks and 78 weeks of udenafil treatment. This change represents persistence of initial effectiveness beyond 26 weeks. For the Placebo/De Novo-Udenafil group, change to Week 52 of FUEL Extension measures change in exercise capacity from pre-udenafil to after 52 weeks of udenafil treatment.

In the Placebo/De Novo-Udenafil group, mean exercise capacity and myocardial performance improved between pre-udenafil and after 52 weeks of udenafil treatment:

- Mean increase at peak exercise effort in VO₂ (58.00 mL/min), work rate (5.78 watts), and minute ventilation (2.41 L/min). When VO₂ was standardized by each subject's body weight, a mean decrease was observed (-0.93 mL/kg/min; 95% CI: -1.7 to -0.2 mL/kg/min).
- Mean increase in VO₂ at VAT of 12.90 mL/min (95% confidence interval [CI]: -23.1 to 48.9 mL/min). When standardized by each subject's body weight, a mean decrease was observed (-0.93 mL/kg/min; 95% CI: -1.5 to -0.4 mL/kg/min).
- Mean decrease in VE/VCO₂ at VAT of -0.77 (95% CI: -1.4 to -0.2).
- Mean increase in work rate at VAT of 0.58 watts (95% CI: -2.6 to 3.7 watts).
- Mean decrease in MPI of -0.04 (95% CI: -0.1 to 0.0).

In the Udenafil-Udenafil group, mean exercise capacity was improved while myocardial performance did not deteriorate between 26 weeks and 78 weeks of udenafil treatment:

- Mean increase at peak exercise effort in VO₂ (38.00 mL/min), work rate (2.99 watts), and minute ventilation (2.56 L/min). When VO₂ was standardized by each subject's body weight, a mean decrease was observed (-1.45 mL/kg/min; 95% CI: -2.3 to -0.6 mL/kg/min).
- Mean increase in VO₂ at VAT of 6.57 mL/min (95% CI: -47.9 to 61.0 mL/min). When standardized by each subject's body weight, a mean decrease was observed (-1.25 mL/kg/min; 95% CI: -2.1 to -0.4 mL/kg/min).
- Mean decrease in VE/VCO₂ at VAT of -0.66 (95% CI: -1.6 to 0.3).
- Mean increase in work rate at VAT of 0.26 watts (95% CI: -5.1 to 5.6 watts).
- Negligible mean decrease in MPI of -0.0 (95% CI: 0.0 to 0.0).

SAFETY RESULTS:

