No subject died during the study. At least 1 serious TEAE was reported by 14 (10.9%) subjects in the Udenafil-Udenafil group and 24 (13.9%) subjects in the Placebo/De Novo-Udenafil group. Among the serious TEAEs reported, cardiac failure was reported by 4 subjects in the Placebo/De Novo Udenafil group, transient ischaemic attack was reported by 2 subjects in the Placebo/De Novo Udenafil group and 1 subject in the Udenafil-Udenafil group, abdominal pain and appendicitis were reported by 2 subjects each in the Udenafil-Udenafil group, protein-losing gastroenteropathy, gastroenteritis, and syncope were reported by 2 subjects each in the Placebo/De Novo Udenafil group, and anaemia, supraventricular tachycardia, ventricular tachycardia, and vomiting were reported by 1 subject each in the Udenafil-Udenafil and Placebo/De Novo Udenafil groups. All other serious TEAEs were reported by no more than a single subject in either treatment group. Hospitalization was reported for 14 (10.9%) subjects in the Udenafil-Udenafil group and for 24 (13.9%) subjects in the Placebo/De Novo Udenafil group. No transplants were reported.

At least 1 TEAE leading to temporary or permanent discontinuation of study drug was reported by 20 (15.6%) subjects in the Udenafil-Udenafil group and 22 (12.7%) subjects in the Placebo/De Novo-Udenafil group. The most common types of TEAEs that led to temporary or permanent discontinuation of study drug were associated with nervous system disorders including headache (2 Udenafil-Udenafil, 4 Placebo/De Novo-Udenafil), migraine (2 Udenafil-Udenafil, 2 Placebo/De Novo-Udenafil), and dizziness (1 Udenafil-Udenafil, 2 Placebo/De Novo-Udenafil). Dizziness was the most commonly reported TEAE of special interest (11.7% Udenafil-Udenafil and 12.7% Placebo/De Novo-Udenafil). None of the events of dizziness was serious, all were considered mild or moderate in intensity and most required no change in study drug. The other TEAEs of interest including syncope, presyncope, and hypotension occurred in <4% of subjects in either treatment group.

No clinically important findings were observed in the evaluations of vital signs.

CONCLUSION:

Improvement in exercise capacity was observed in those who were previously naïve to udenafil therapy, and there was persistence of effect on exercise capacity for those who were previously treated with udenafil. Udenafil administered orally at 87.5 mg BID for 52 weeks was safe and well tolerated in this study.

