9.8.2 Changes to Planned Analyses

9.8.2.1 Changes Between Protocol Finalization and Final Statistical Analysis Plan

The SAP was finalized 23 June 2016. Key changes to statistical analyses between protocol finalization and the final SAP are described below.

The protocol defined 2 non-ITT analysis populations. The SAP replaced these non-ITT analysis populations by defining the more traditional Per Protocol population. In addition, the SAP provided a definition for the Safety population.

The protocol stated that potential differential impact of continuous age on treatment outcomes would be assessed and that a treatment by subpopulation interaction test would be conducted to identify differential treatment effects. Tests for treatment by subpopulation were not performed due to the low power of the tests.

The protocol also stated that treatment group differences would be assessed within subpopulations if the interaction p-value was <0.10 . These tests were not performed due to their potentially low power and bias due to lack of randomization within each subpopulation.

Minor clarifications were made to imputations for missing values.

Differences between the SAP and analyses presented in the clinical study report include:

- Presentation of the following for exercise capacity:
 - Percent predicted maximal VO_2
 - Heart rate at peak exercise
- Additional specific variables related to ventricular performance were summarized in the statistical tables.
- Friedman's test using ventricular morphology (single left versus single right or mixed) as the stratification factor was not used to assess treatment group differences for endpoints associated with the PedsQL and PCQLI. Differences were assessed using the same ANCOVA model as the other secondary endpoints.
- The qualitative estimate of atrioventricular valve insufficiency was not assessed.

- Subgroup analyses of AEs were also performed for gender, race, and ethnicity.
- Descriptive statistics of udenafil and metabolite concentrations were provided.

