11.4.1.4 Secondary Efficacy Endpoints

11.4.1.4.1 Secondary Efficacy Endpoints Measured at Ventilatory Anaerobic Threshold

The 2 secondary efficacy endpoints measured at VAT indicated greater exercise capacity in the udenafil group than the placebo group at Week 26:

- VE/VCO₂ at VAT: Greater mean decrease (improvement) for udenafil (-0.76) as compared to placebo (-0.05) at Week 26 (p=0.011)
- Work rate at VAT: Greater mean increase (improvement) for udenafil (3.46 watts) as compared to placebo (0.31 watts) at Week 26 (p=0.029)

Change in secondary exercise endpoints measured at VAT from baseline to Week 26 are summarized in [Table 17](#).

Table 17: Difference in Secondary Exercise Endpoints Measured at Ventilatory Anaerobic Threshold Between Week 26 and Baseline Visits Using Last Observation Carried Forward (ITT Population)

Exercise Endpoint	Udenafil (N=200)	Placebo (N=200)	Difference LS Mean (SE)	p-value
VE/VCO₂ at VAT				
Baseline	n=170	n=181		
Mean (SD)	34.32 (4.845)	34.75 (5.157)	-0.42 (0.536)	0.431 ^a
Week 26	n=185	n=191		
Mean (SD)	33.60 (4.833)	34.67 (4.872)	-1.13 (0.509)	0.027 ^a
Difference, Week 26 – baseline	n=170	n=181		
Mean (SD)	-0.76 (3.564)	-0.05 (2.967)	-0.82 (0.321)	0.011 ^b
Median	0.00	0.00		
Work rate at VAT (watts)				
Baseline	n=167	n=177		
Mean (SD)	66.19 (26.321)	66.10 (23.446)	0.12 (2.688)	0.963 ^a
Week 26	n=181	n=186		
Mean (SD)	69.20 (26.171)	66.62 (22.710)	3.30 (2.660)	0.215 ^a
Difference, Week 26 – baseline	n=167	n=177		
Mean (SD)	3.46 (15.076)	0.31 (13.246)	3.20 (1.460)	0.029 ^b
Median	1.00	0.00		

ANCOVA=analysis of covariance; ANOVA=analysis of variance; ITT=intent-to-treat; LS=least squares; SD=standard deviation; SE=standard error; VAT=ventilatory anaerobic threshold; VE/VCO₂=ventilatory equivalents of carbon dioxide; VO₂=minute oxygen consumption

a P-value was assessed using ANOVA with fixed factors for ventricular morphology (single left versus single right or mixed) and treatment group.

b P-value was assessed using ANCOVA with fixed factors for ventricular morphology (single left versus single right or mixed) and treatment group with a continuous covariate of baseline maximal VO₂.

Source: [Table 14.2.13.1.1](#) and [Table 14.2.14.1.1](#)

Program: [T_14_2_13_1_1.sas](#) and [T_14_2_14_1_1.sas](#)

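### The extension synopsis concludes that udenafil-naive subjects improved in exercise capacity, but its uncontrolled and conflicting results do not establish this

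*Protocol*

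**What the plan says.** The extension was open label with one regimen. Its synopsis gives "Reference therapy, dose and mode of administration, batch number: None" and states "All summaries were descriptive", with a two-sided 95% CI for within-group change. The naive group combines subjects who took placebo in FUEL with De Novo subjects. For them the measured quantity is "change in exercise capacity from pre-udenafil to after 52 weeks of udenafil treatment".

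The synopsis conclusion says, without qualification, "Improvement in exercise capacity was observed in those who were previously naïve to udenafil therapy". The lead-in to the naive-group results says the same of mean exercise capacity.

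The bullets below that lead-in open with three unscaled peak gains: VO2 +58.00 mL/min, work rate +5.78 W and minute ventilation +2.41 L/min. None has an interval. For weight-standardised VO2 at peak they report that "a mean decrease was observed (-0.93 mL/kg/min; 95% CI: -1.7 to -0.2 mL/kg/min"; at VAT, "a mean decrease was observed (-0.93 mL/kg/min; 95% CI: -1.5 to -0.4 mL/kg/min". They also give:

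- unscaled VO2 at VAT: +12.90 mL/min (CI -23.1 to 48.9)
- work rate at VAT: +0.58 W (CI -2.6 to 3.7)
- VE/VCO2 at VAT: -0.77 (CI -1.4 to -0.2)

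The SAP supplied covers the 26-week FUEL trial and does not plan the extension's analysis.

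**The concern.** The conclusion reads a one-year before-after change in adolescents as improvement. VO2 changes direction with scaling: up in mL/min at peak, down per kg at peak and at VAT, with both per-kg intervals wholly below zero. The conclusion mentions neither fall.

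The measures taken at VAT matter particularly, because section 11.4.7 argues that VO2 at VAT is the more useful endpoint in Fontan patients. On the unscaled version of that endpoint the naive group shows no clear change.

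At stake is whether the extension is read as independent support for efficacy in naive subjects. This point does not concern the separate persistence statement for subjects already treated in FUEL.

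**Working it through.** **1. Reproducing stated figures.** FUEL Table 18 gives treatment differences of 0.19 W (SE 1.363, p=0.891) for peak work rate and 0.14 L/min (SE 1.319, p=0.915) for minute ventilation.

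- Work rate: t = 0.19/1.363 = 0.139, about 393 df, p = 0.889. An unrounded 0.185 gives 0.892, so 0.891 is reproduced within rounding.
- Ventilation: t = 0.14/1.319 = 0.106, p = 0.916, also within rounding.

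The extension intervals can be checked only by midpoint, because the synopsis gives no efficacy n or SD. The midpoints are -0.95 against -0.93 (both per-kg measures), 12.90 against 12.90, -0.80 against -0.77, and 0.55 against 0.58. All are consistent with bounds rounded to one decimal.

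**2. Naive group beside FUEL placebo.** Placebo means, SDs and n come from Tables 13, 15, 17 and 18. Placebo intervals are mean ± t × SD/√n. For example, peak work rate is 2.45 ± 1.972 × 13.503/√199 = 2.45 ± 1.89. The durations differ.

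| Measure | Naive group, 52 weeks (95% CI) | FUEL placebo, 26 weeks (95% CI) |
|---|---|---|
| Peak VO2, mL/min | +58.00 (not given) | -3.65 (-34.7 to 27.4) |
| Peak VO2, mL/kg/min | -0.93 (-1.7 to -0.2) | -0.89 (-1.40 to -0.38) |
| Peak work rate, W | +5.78 (not given) | +2.45 (0.56 to 4.34) |
| Peak minute ventilation, L/min | +2.41 (not given) | -0.10 (-2.02 to 1.82) |
| VO2 at VAT, mL/min | +12.90 (-23.1 to 48.9) | -8.01 (-34.9 to 18.8) |
| VO2 at VAT, mL/kg/min | -0.93 (-1.5 to -0.4) | -0.68 (-1.15 to -0.21) |
| Work rate at VAT, W | +0.58 (-2.6 to 3.7) | +0.31 (-1.65 to 2.27) |
| VE/VCO2 at VAT | -0.77 (-1.4 to -0.2) | -0.05 (-0.49 to 0.39) |

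The placebo figures use last observation carried forward, which pulls changes toward zero.

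**3. What the placebo arm shows about rival explanations.**

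- *Peak work rate.* Untreated subjects gained, and randomised treatment made no detectable difference (0.19 W). If the placebo gain is assumed linear in time, 2 × 2.45 = 4.90 W (1.12 to 8.68), which contains 5.78. If it is assumed to stop at 26 weeks, 2.45 W (0.56 to 4.34) excludes 5.78. The documents do not say which assumption applies.
- *Unscaled peak VO2 and ventilation.* Placebo did not gain on either. Its implied mean weight nevertheless rose from 1626.95/28.01 = 58.1 kg to 1623.30/27.12 = 59.9 kg, about +1.8 kg.
- *Per-kg peak VO2.* Placebo fell 0.89 in 26 weeks and the naive group 0.93 in 52 weeks, so the extension's fall is no faster.

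**4. Scale of possible growth.** The synopsis gives no extension baseline, so FUEL placebo values are assumed.

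- FUEL baseline: (1626.95 + 58)/(28.01 - 0.93) = 62.2 kg, a gain of 4.1 kg (7.1%).
- FUEL Week 26: (1623.30 + 58)/(27.12 - 0.93) = 64.2 kg, a gain of 4.3 kg (7.3%).

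The VO2 gain is 58/1626.95 = 3.6% (also 3.6% from the Week 26 value). These are ratios of means and therefore approximate. On these assumptions weight rose about twice as much, proportionally, as VO2.

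**The case against.** Much is disclosed. The per-kg falls stand in the same bullets as the gains, the absence of a comparator is stated, and the conclusion says improvement was observed without naming the drug as its cause. That removes any suggestion of concealment. It does not make the summary sentence a fair account of mixed results.

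Per-kg VO2 is also a disputed scale. Section 9.8.2.3 notes that weight gain lowers it even when absolute VO2 is unchanged. That stands, and it is a reason not to treat either scale as decisive.

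VE/VCO2 at VAT is the strongest contrary result. It improved with an interval below zero, while FUEL placebo barely moved. It must be reported. A single uncontrolled ventilatory measure still cannot settle exercise capacity while VO2 changes sign with scaling. The myocardial performance index also moved favourably (-0.04), but it measures ventricular function.

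Only the extension synopsis is supplied; from section 5 the body reports FUEL. Caveats in a full extension report cannot be checked.

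Two stronger readings are tempting:

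- A reader might infer that growth or familiarity with the test accounts for the gains. The work-rate comparison sets 26 weeks against 52 and needs an assumed linear trend. Placebo unscaled peak VO2 and ventilation did not rise at all.
- A reader might infer that naive subjects declined as fast as the natural history in section 9.5.2 (up to 2.6% per year). That figure is introduced alongside percent-of-predicted values, and placebo per-kg VO2 fell almost as much in half the time.

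**Conclusion.** The conclusion is not established; the documents do not show it to be false. Three facts carry this without extrapolation: there is no concurrent control; VO2 rises or falls according to scaling, with both per-kg intervals below zero; and the unscaled VAT measures are compatible with no change. FUEL's null randomised comparisons for peak work rate and minute ventilation weaken two of the three headline gains further.

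Growth and repeat testing remain plausible but undemonstrated. The implied weight gain of about 4.1 to 4.3 kg rests on assumed FUEL-like baselines, and any per-year reading of the placebo arm rests on an assumed time course. The finding depends on neither. The text should be corrected because the sentence is a headline efficacy conclusion and the correction costs little.

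**What to change.** Replace the conclusion sentence, and the exercise-capacity statement in the lead-in to the naive-group results, with:

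> In udenafil-naive subjects, over 52 weeks absolute peak VO2 rose by 58 mL/min and VE/VCO2 at VAT fell by 0.77 (CI -1.4 to -0.2), while weight-standardised VO2 at peak and at VAT fell (CIs below zero) and unscaled VO2 and work rate at VAT showed no clear change; without a concurrent control, no effect of udenafil on exercise capacity can be concluded.

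Give the 95% CIs for the three unscaled peak measures, which the synopsis methods say were calculated. Show the FUEL placebo 26-week change beside every naive-group measure, favourable and unfavourable alike, labelled as a different duration.

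Percent-predicted maximal VO2 was an addition beyond the SAP in FUEL (section 9.8.2.1) and is not among the extension endpoints listed in the synopsis. If available, it may be added only as a labelled post hoc measure.

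The cost is revised text, intervals already calculated and one column of existing FUEL results. The downside for the sponsor is a less favourable efficacy statement.
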